5.3.3. DLT-Evaluable Population in Dose Escalation

The DLT-evaluable population in the dose-escalation part will include participants treated with the assigned dose level of INCB001158 who have had a DLT or those who have received at least 75% of the planned doses (ie, \geq 32 of the maximum 42 doses to be given in a 21-day cycle or \geq 42 of the maximum 56 doses to be given in a 28-day cycle). For participants in Part 1b, participants must receive the planned doses of pembrolizumab in Cycle 1 in order to be evaluable for DLTs. This population will be considered evaluable for determining the tolerability of the given dose.

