### 5.1.1 Dose Escalation Rules and Definition of Maximally Tolerated Dose (MTD)

Dose limiting toxicities (DLTs) observed in the first 28 days of dosing for monotherapy dose escalation (Part 1a) or the first 42 days of dosing for combination dose escalation (Part 1b) will be used to determine escalation to the next dose level. The study is using a traditional 3+3 design and the dose escalation rules are as follows:

- An initial cohort of 3 patients is enrolled.
- If 0/3 patients develops a DLT, escalation to the next dose will occur.
- If 1/3 patients develops a DLT:
  - Another 3 patients will be enrolled at this dose level.
    - If 0 of the 3 new patients develops a DLT (for a total of 1/6 patients with a DLT at this dose level), escalation to the next dose level will occur.
    - If  $\geq 1$  of the 3 new patients develops a DLT (for a total of  $\geq 2/6$  patients with a DLT at this dose level), the dose escalation stage of the trial will be terminated, and the dose directly below the current dose will be considered the MTD.
- If  $\geq 2/3$  patients develop a DLT, the dose escalation stage of the trial will be terminated, and the dose directly below the current dose will be considered the MTD.

If a dose level below 1000 mg BID is selected as the MTD on the basis of only 2 DLTs and subsequent clinical data [e.g., in the expansion cohort(s)] demonstrate that the rate of AEs that qualify as DLTs at that dose level is  $< 10\%$  in  $> 10$  patients, re-escalation to the next dose level previously associated with DLTs may be considered. If re-escalation occurs, up to 6 additional patients may be enrolled and the dose level may be considered tolerable if the overall DLT rate for that dose level is  $\leq 25\%$ .

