### 5.1.2 Dose-Limiting Toxicity

During dose escalation, patients must receive at least 75% of the planned INCB001158 administrations (Parts 1a and 1b) and two doses of pembrolizumab (Part 1b only) in the DLT evaluation window to be considered evaluable for DLT, unless the patient has a DLT or has the study treatment held for an adverse event (AE) that may herald a DLT. The DLT evaluation window will be the first 28 days (Part 1a) or the first 42 days (Part 1b) on study, starting from Cycle 1 Day 1 (C1D1). Patients who discontinue the study during the DLT evaluation window prior to receiving the requisite study treatment administrations for reasons that include, but are not limited to, clinical/radiographic progression, voluntary withdrawal, or complications that the

Principal Investigator considers secondary to the patient's malignancy will not be considered evaluable for DLT and will be replaced. In addition to DLTs, a pharmacokinetic threshold of 100  $\mu\text{g}\cdot\text{hr}/\text{mL}$  is included as a dose-limiting event. This is an exposure that was well tolerated in preclinical species and exceeds the expected efficacious exposure by 14-fold.

During Part 1b, it is likely that Grade 3 AEs associated with pembrolizumab administration will occur and, given the small sample size of cohorts, this could occur by chance in 2 of 6 patients, the usual threshold for unacceptable toxicity. It will be important to differentiate between immune-related adverse events (irAEs) expected from pembrolizumab toxicity as opposed to an increase in frequency or a worsening of severity of irAEs as an indicator of unacceptable toxicity related to the combination. Dose escalation cohorts can be expanded up to 12 patients if DLTs occur that are expected pembrolizumab-related irAEs per the pembrolizumab product label.

The Common Terminology Criteria for Adverse Events (CTCAE v4.03) will be used to identify and classify toxicities arising during the study. The occurrence of any of the following toxicities during Cycle 1 will be considered a DLT, if judged by the Investigator to be related (possibly or probably) to administration of either or both study treatment(s):

Non- Hematologic DLTs:

- Any  $\geq$  Grade 4 non-hematological toxicity
- Grade 3 non-hematologic toxicity lasting  $> 3$  days despite optimal supportive care with the exception of:
  - Grade 3 fatigue lasting  $\leq 7$  days
  - Grade 3 rash that resolves to  $\leq$  Grade 1 within 3 weeks

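### For Part 1b, SAP 5.3.3 tests DLT evaluability over one 21-day cycle and one pembrolizumab infusion, where the protocol uses 42 days and two infusions; the effect is limited to a flag and a count

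*SAP*

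**What the plan says.** **SAP.** Section 5.3.3 admits to the DLT-evaluable population anyone who had a DLT. It also admits anyone who took at least 75% of planned INCB001158 doses, spelled out as at least "32 of the maximum 42 doses to be given in a 21-day cycle" or 42 of 56 in a 28-day cycle. For Part 1b it adds that "participants must receive the planned doses of pembrolizumab in Cycle 1 in order to be evaluable for DLTs". It gives the purpose as follows: "This population will be considered evaluable for determining the tolerability of the given dose". Section 9.1, on changes to protocol-defined analyses, reports none.

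**Protocol.** Under Section 5.1.1, DLTs in "the first 42 days of dosing for combination dose escalation (Part 1b) will be used to determine escalation to the next dose level". Section 5.1.2 repeats this: "The DLT evaluation window will be the first 28 days (Part 1a) or the first 42 days (Part 1b) on study". Within that window, "patients must receive at least 75% of the planned INCB001158 administrations (Parts 1a and 1b) and two doses of pembrolizumab (Part 1b only"), "unless the patient has a DLT or has the study treatment held for an adverse event (AE) that may herald a DLT". Patients who leave before reaching those minimums, for reasons such as progression or withdrawal, "will not be considered evaluable for DLT and will be replaced". Section 15.3.2, the protocol's own paragraph on the DLT-evaluable population, asks for 43 of 56 doses in 28 days and, for Part 1b, both pembrolizumab doses. It places both in Cycle 1, which has only one infusion.

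**The concern.** In dose escalation, a patient without a DLT supports a dose level only if observed and treated for long enough. The protocol sets that length for the combination at two 21-day cycles with two infusions. The SAP halves it without saying so.

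A patient who stops early without a DLT would be flagged evaluable by the SAP although the protocol treats that patient as uninformative and enrols a replacement; the SAP would then count both. The protocol's safety statement for the combination (Section 10.2.2.1) is that no DLTs were seen at 100 mg BID, so the number of patients properly observed is what gives that statement its weight. An evaluable count that includes patients followed for less than half the window would overstate it.

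**Working it through.** **Inputs.** INCB001158 is taken twice daily on every day of each 21-day cycle in Part 1b. The single-dose first day applies only to Parts 1a and 1c (Protocol 11.2.1.1), so a fully adherent Part 1b patient has taken 2d doses by the end of Day d. Pembrolizumab is given on Day 1 of each 21-day cycle (SAP 4.1.5; Protocol Attachment 1B), nominally Days 1 and 22. Part 1a has 28-day cycles, so among the escalation parts the SAP's 21-day figure can only refer to Part 1b.

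**Thresholds.** Planned doses = 2 × days; minimum = 75% of planned, rounded up. The SAP's own figures reproduce: 0.75 × 42 = 31.5, so 32; 0.75 × 56 = 42. The figure 63 of 84 is printed nowhere; it follows from 5.1.2 as 0.75 × 84.

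| | SAP 5.3.3 | Protocol 5.1.2 | Protocol 15.3.2 |
|---|---|---|---|
| Basis | 21 days | 42 days | 28 days |
| Planned doses | 42 | 84 | 56 |
| Minimum doses | 32 | 63 | 43 (as printed) |
| Infusions | 1 | 2 | 2 |
| Dose minimum reached, full adherence | Day 16 (2 × 16 = 32) | Day 32 (62 doses by end of Day 31) | Day 22 (42 doses by end of Day 21) |

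The SAP minimum is 32/84 = 38.1% of the doses planned in the 42-day window, and 16/42 = 38.1% of its days.

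**Evaluable under the SAP, not under the protocol** (fully adherent, no DLT):
- Last dose on Days 16 to 21 (6 days): fails both protocol sections, on doses and on infusions.
- Last dose on Days 22 to 31: fails 5.1.2 on doses, but can meet 15.3.2. Against 5.1.2 alone the range is therefore Days 16 to 31 (16 days).

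**Evaluable under the protocol, not under the SAP** (both infusions given, no DLT). Take k doses in Cycle 1 and all 42 in Cycle 2:
- 5.1.2 needs k + 42 ≥ 63, so k ≥ 21; the SAP needs k ≥ 32. Discordant for k = 21 to 31, that is 63 to 73 of 84 doses (75.0% to 86.9%).
- If the 43-dose rule of 15.3.2 is applied as well, doses by Day 28 are k + 14 ≥ 43, so k ≥ 29. Discordant only for k = 29 to 31.

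**Effect on a count.** Let m patients at a dose level be early leavers of the first kind. If they are replaced, the SAP counts 6 + m where the protocol counts 6; if not, it counts 6 where the protocol counts 6 − m. The excess is m either way, less any patients of the second kind. For illustration, m = 1, 2 or 3 with replacement gives 7, 8 or 9 instead of 6. The documents do not give m, and it may be 0.

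**The case against.** **The protocol does not state one rule.** Section 15.3.2 is the paragraph the SAP would naturally implement. Its 43 doses in 28 days differ from 5.1.2, and 5.1.2 itself ties its list of DLTs to Cycle 1 despite its 42-day window. This stands in part: it narrows the range that conflicts with every protocol rule to Days 16 to 21, and it shrinks the reverse case. It does not rescue the SAP. Section 15.3.2 still demands two infusions and contains no 32-of-42 rule, so the SAP matches neither section.

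**The omitted exception matters little.** The SAP leaves out patients whose treatment was held for an AE that may precede a DLT. Protocol 5.1.2 makes failure to reach the dose minimums because of a drug-related AE a DLT in itself, and the SAP admits everyone with a DLT. Most such patients therefore enter the population anyway. This stands.

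**Nothing planned is shown to rest on this population.** SAP 5.3.2 runs all safety analyses on the safety population, and SAP 8.2.2 only lists DLTs by dose level. The table shells are not in the documents, so it is unknown whether a DLT-evaluable count will be printed. This stands, and it limits the size of the point.

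**A stronger reading.** A reader might infer that the combination dose was chosen on the wrong patients, or that a DLT rate will be biased. The documents do not support either. Evaluability and replacement during escalation were governed by the protocol. The protocol version that the SAP cites already reports the combination RP2D as declared at 100 mg BID, and the SAP is dated 22 FEB 2021. No DLT rate or interval is planned. A patient with a DLT is evaluable whatever the dose count, so the SAP's dose threshold cannot change the DLT listing.

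**Conclusion.** The mismatch is real, undisclosed and minor. For Part 1b, SAP 5.3.3 sets evaluability on one cycle and one infusion, against 42 days and two infusions in Protocol 5.1.1 and 5.1.2. A fully adherent, DLT-free patient with a last dose on Days 16 to 21 is classified differently from both protocol sections; under 5.1.2 alone, Days 16 to 31. The reverse misclassification covers 21 to 31 Cycle 1 doses under 5.1.2, or 29 to 31 if 15.3.2 is also applied.

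The consequence is limited to the DLT-evaluable flag and any evaluable count reported from it, in the Analysis Populations tables (1.1.1.2 covers Part 1b) or Listing 2.3. The day ranges assume nominal visit days and full adherence; the reverse case assumes a complete Cycle 2 and both infusions.

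**What to change.** In SAP 5.3.3, define a Part 1b participant as DLT-evaluable if they had a DLT, or received at least 63 of 84 INCB001158 doses and two pembrolizumab infusions within the 42-day window. Carry over the Protocol 5.1.2 exception for treatment held for an AE that may precede a DLT, for consistency. State that the Part 1b window is 42 days. Re-derive the flag and report the evaluable count for each Part 1b dose level.

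The cost is one paragraph in the SAP, one re-derived flag, and a re-run of the Analysis Populations tables and Listing 2.3 with the count added. No new data and no protocol amendment are needed. The wording of Protocol 15.3.2, and the Cycle 1 limit on the DLT list in 5.1.2, should be aligned only if the protocol is next amended for another reason.

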5.3.4. Efficacy-Evaluable Population

See Protocol Section 15.3.3. The efficacy-evaluable population will be used for the analysis of efficacy data except PFS.

6. **BASELINE, EXPOSURE, AND DISPOSITION**

Appendix A provides a list of data displays. Sample data displays are included in a separate document.

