#### **11.4 End of Treatment (EOT)**

The End of Treatment (EOT) visit must occur within 28 days of treatment discontinuation and prior to initiation of any new anti-cancer therapy/regimen. All patients discontinuing study treatment for any reason should undergo the following EOT procedures:

- AE monitoring
- Recording of concomitant medications
- Vital signs and weight
- Complete physical examination
- ECOG performance status evaluation
- Clinical laboratory values (hematology, coagulation, serum chemistry and urinalysis)
- Urine pregnancy test for women of child-bearing potential
- Duplicate 12-lead ECG with QTcF
- Radiographic evaluation (e.g., diagnostic CT or MRI) of tumor burden. Patients who discontinue from study due to objective findings of progressive disease during an on-treatment evaluation do not need to have repeat scans. CT or MRI is required for all patients who have not had at least 1 post-baseline image.

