#### **15.3.3 Efficacy Evaluable Populations**

The Response Evaluable Population includes all patients who received at least 1 dose of study treatment (INCB001158 or pembrolizumab), completed a baseline scan, and met at least 1 of the following criteria:

- The patient had at least 1 post-baseline scan.

- The patient discontinued from study treatment for any reason except unrelated toxicity or death, or withdrawal of consent.

The PFS Evaluable Population includes all patients who received at least 1 dose of study treatment (INCB001158 or pembrolizumab).

Patients enrolled in the expansion cohorts who do not meet the requirements for the Response Evaluable Population will be considered non-evaluable for response and will be replaced.

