#### 15.4 Efficacy Analysis

Response to treatment will be evaluated using RECIST v1.1 for patients with solid tumors (except for mesothelioma; [Eisenhauer 2009](#)). For patients with pleural mesothelioma, response will be evaluated using the modified RECIST criteria for pleural mesothelioma ([Byrne 2004, Attachment 5](#)). Responses for patients with pericardial or peritoneal mesothelioma will be described based upon RECIST v1.1 for patients with measurable disease combined with clinical improvements.

The Kaplan-Meier method will be used to estimate the median Duration of Response (DOR) and Progression-Free Survival (PFS) for each treatment cohort in Dose Expansion (note: Dose Escalation patients of the same histology enrolled at the RP2D will be included in this analysis). Efficacy analyses will be performed on the Efficacy Evaluable Population. Additional efficacy analyses will also be performed on an expanded population that includes patients that lack post-treatment scans due to toxicity or death.

For each patient with objectively measurable disease, response to therapy, will be calculated using RECIST v1.1 and Modified RECIST for pleural mesothelioma (DOR, PFS, Best Overall Response [BOR], and Overall Response Rate[ORR]).

- DOR is defined as the number of days from the date of initial response (PR or better) to the date of first documented disease progression/relapse or death, whichever occurs first.
- PFS is defined as the number of days from the date of treatment initiation (i.e., C1D1) to the date of documented disease progression or death from any cause, whichever occurs first, and will be calculated for all patients. In the event that no disease progression or death is documented prior to study termination, analysis cutoff, or the start of confounding anticancer therapy, these endpoints will be censored at the date of last available tumor assessment.

- BOR is the best RECIST v1.1 /modified RECIST for pleural mesothelioma response recorded from the start of the study treatment until disease progression/recurrence.
- ORR is defined as the response of the proportion of efficacy evaluable patients with tumor size reduction from the time the start of treatment until documented tumor progression. ORR includes complete response (CR) and partial response (PR).

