2. STUDY INFORMATION, OBJECTIVES, AND ENDPOINTS

2.1. Protocol and Case Report Form Version

This SAP is based on INCB 01158-101 Protocol Amendment 2-US 3 dated 10 NOV 2020 and CRFs approved 08 APR 2019. Unless superseded by an amendment, this SAP will be effective for all subsequent protocol amendments and eCRF versions.

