5.3. Analysis Populations

5.3.1. Full Analysis Set

The FAS will include all participants who received at least 1 dose of INCB001158 or pembrolizumab. Participants will be analyzed according to the treatment to which they have been initially assigned.

The FAS will be used for the summary of demographics, baseline characteristics, participant disposition, and analyses of PFS.

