7.3.3. Objective Response Rate

A participant is considered an objective responder if they have a best overall response of CR or PR before first PD and start of any subsequent anticancer therapy.

The ORR based on both unconfirmed and confirmed best overall responses will be estimated with 95% CIs. Confidence intervals will be calculated based on the exact method for binomial distributions.

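### The SAP drops, without declaring it, the expanded-population efficacy analysis that Protocol 15.4 commits to; ORR and BOR are planned only on the efficacy-evaluable set

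*SAP*

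**What the plan says.** Protocol 15.4 makes the efficacy-evaluable set the main efficacy population and then adds: "Additional efficacy analyses will also be performed on an expanded population that includes patients that lack post-treatment scans due to toxicity or death".

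Protocol 15.3.3 decides who is response-evaluable. A treated patient with a baseline scan qualifies either by having a post-baseline scan or by this criterion: "The patient discontinued from study treatment for any reason except unrelated toxicity or death, or withdrawal of consent". Expansion-cohort patients who do not qualify "will be considered non-evaluable for response and will be replaced".

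The SAP works from the same protocol version: "This SAP is based on INCB 01158-101 Protocol Amendment 2-US 3 dated 10 NOV 2020". Its section 5.3 defines four populations: full analysis set (FAS), safety, DLT-evaluable and efficacy-evaluable. Section 5.3.4 refers to Protocol 15.3.3 and says: "The efficacy-evaluable population will be used for the analysis of efficacy data except PFS". The wider all-treated set has other uses: "The FAS will be used for the summary of demographics, baseline characteristics, participant disposition, and analyses of PFS". Section 7.3.5 also uses it for best percentage change in target lesions and the waterfall plot.

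Section 7.3.3 says: "The ORR based on both unconfirmed and confirmed best overall responses will be estimated with 95% CIs". It names no second population. In Appendix A, the four confirmed tables (2.1.1.1.1 to 2.1.1.1.4) and the four unconfirmed tables (2.1.1.3.1 to 2.1.1.3.4) for ORR and BOR are all on the efficacy-evaluable population. Section 9.1, the place for changes to protocol-defined analyses, is marked as not applicable.

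**The concern.** The protocol states the extra analysis as a commitment, not an option. A SAP based on the same amendment should either specify it or say that it has been dropped, and this one does neither.

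The omission works in one direction. Patients who left early through unrelated toxicity or death, with no post-baseline scan, are taken out of the response denominator and, in the expansion cohorts, replaced. The expanded analysis is the check that shows how much this raises the reported ORR. Without it, only the equal-or-higher figure is tabulated, and a reader of SAP 9.1 would believe that nothing had changed.

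**Working it through.** **1. The plan's own design figures.** Protocol Table 15.2-1 gives the Simon designs as n1 (r1) and n (r2), with nominal one-sided alpha 0.1 and power 80%. The exact probability of passing at response rate p is the sum, over x from r1+1 to n1, of P(X1 = x) × P(X2 ≥ r2+1−x), with X1 ~ Bin(n1, p) and X2 ~ Bin(n−n1, p).

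| Cohorts | Stage 1, total | p0, p1 | Exact alpha | Exact power |
|---|---|---|---|---|
| 2a, 2b, 2c expansion, 3a–3e | 11 (0), 26 (1) | 2%, 15% | 0.0665 | 80.4% |
| 3f | 13 (1), 34 (5) | 10%, 25% | 0.0957 | 81.1% |
| 3g | 12 (2), 25 (7) | 20%, 40% | 0.0991 | 81.5% |
| 3h | 10 (1), 33 (6) | 13%, 30% | 0.0972 | 80.1% |

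The stated figures are reproduced. These rules count response-evaluable patients, so the missing analysis does not affect them.

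**2. Which endpoints the Protocol 15.4 sentence can affect.**

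- PFS: the protocol's PFS set is already all treated patients, and the SAP uses the FAS. There is nothing to expand.
- DOR: responders only (SAP 7.3.4). Unscanned patients cannot enter.
- Best percentage change: on the FAS, but a patient with no post-baseline scan contributes no value.
- ORR and BOR: the denominator changes. None of the eight planned tables uses a wider set.

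**3. Who would be added.** Patients who stopped for related toxicity without a scan are already response-evaluable under Protocol 15.3.3. It is unclear whether 'unrelated' in that criterion also qualifies 'death'. If it does, unscanned treatment-related deaths are already in the set; if not, every unscanned death is out. On either reading the patients added back have no post-treatment scan and cannot be responders.

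**4. Direction.** With x responders among n evaluable patients and k patients added back, the planned ORR is x/n and the expanded ORR is x/(n+k). Since k ≥ 0, the planned figure is never the lower one.

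**5. Size.** The documents give no k, so k = 1, 2 and 3 are assumptions. Each design is taken at its smallest passing count, x = r2+1. Intervals are exact (Clopper-Pearson) 95%.

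| Design | k = 0 (95% CI) | k = 1 | k = 2 | k = 3 (95% CI) | Fall at k = 3 |
|---|---|---|---|---|---|
| 3g | 8/25 = 32.0% (14.9–53.5) | 30.8% | 29.6% | 8/28 = 28.6% (13.2–48.7) | 3.4 points |
| 3h | 7/33 = 21.2% (9.0–38.9) | 20.6% | 20.0% | 7/36 = 19.4% (8.2–36.0) | 1.8 points |
| 3f | 6/34 = 17.6% (6.8–34.5) | 17.1% | 16.7% | 6/37 = 16.2% (6.2–32.0) | 1.4 points |
| 2%/15% cohorts | 2/26 = 7.7% (0.9–25.1) | 7.4% | 7.1% | 2/29 = 6.9% (0.8–22.8) | 0.8 points |

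For a wider range, k = 5 in 3g gives 8/30 = 26.7% (12.3–45.9).

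**The case against.** The strongest reply is that Protocol 15.4 never says the expanded analysis is of ORR. The sentence names no endpoint, follows the text on Kaplan-Meier DOR and PFS, and sits in a section that defines ORR as a proportion of efficacy-evaluable patients. The protocol also says only that the expanded population includes the unscanned patients. The FAS does include them, and the SAP uses it for PFS and the waterfall plot.

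Other points concern importance. Few patients may be affected, because related-toxicity stops stay in and the end-of-treatment visit has this rule: "CT or MRI is required for all patients who have not had at least 1 post-baseline image". Planned disposition tables and listings would let a reader identify the patients, and Appendix A calls its table lists guidelines. Any shift is small beside intervals nearly 40 points wide. Eight more tables, some for small dose-level groups, may be more than is needed.

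Part of this stands. The protocol does not name the endpoint or fully define the set, the number of patients is unknown, and the effect may be nil. The reply does not close the gap. PFS, DOR and the waterfall plot cannot carry the commitment, for the reasons in step 2 of the working, so ORR and BOR are where it has effect. Reading the population more broadly does not help either, since no wider set is used for ORR or BOR anywhere in the SAP. The FAS count is not an exact stand-in for the set described, because it also holds unscanned patients who withdrew consent. Freedom to adjust a table list neither defines a missing population nor corrects section 9.1.

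**Conclusion.** The concern holds. The SAP omits an analysis to which its governing protocol commits, declares no change, and tabulates only the ORR that is equal to or higher than the omitted one.

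The consequences are limited. SAP 3.2 calls all analyses exploratory, SAP 7.1 states that there is no primary efficacy endpoint, and the Simon decisions, type I error and sample size stay as they are. With one to three patients assumed per cohort, the fall in ORR at the smallest passing count ranges from 0.3 points (2/26 to 2/27, 7.7% to 7.4%) to 3.4 points (3g). These sizes rest wholly on the assumed k; the direction does not. It should be fixed before the analysis is run.

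**What to change.** - In SAP 5.3, define the Protocol 15.4 expanded population as the efficacy-evaluable patients plus treated patients who lack post-treatment scans because of toxicity or death. State how the exclusion for unrelated toxicity or death in Protocol 15.3.3 is to be read.
- In SAP 7.3.3 and Appendix A, add ORR and BOR on that population beside the efficacy-evaluable result, with exact 95% confidence intervals for ORR. Count patients without a post-baseline scan as non-responders.
- State that the Simon cut-offs are not re-applied to the enlarged set.
- If the analysis is being dropped on purpose, say so in SAP 9.1 and give the reason.

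The cost is SAP wording and at most eight further ORR/BOR tables from data already collected. The supplementary ORRs may come out slightly lower. No extra patients are needed and no decision rule changes.

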***Part 3f: INCB001158 in combination with pembrolizumab in PD-1/PD-L1 naïve patients with Gastric/GEJ cancer.***

This cohort will enroll patients with advanced/metastatic gastric/GEJ cancer that have never received prior therapy with anti-PD-1/PD-L1, anti-CTLA4 or any other agent that specifically targets an immune checkpoint or co-stimulation pathway.

All patients will have testing for microsatellite stability performed on tumor tissue, either archival or a fresh biopsy. It is expected that ~80-90% of patients will have MSS gastric cancer

(Kim 2013). The primary endpoint will be ORR in patients with MSS disease, since historical data suggests a low ORR in response to anti-PD-1 therapy (Topalian 2012, Brahmer 2010). Patients with MSI will also be followed but will not be considered for the primary endpoint for this cohort. Predose and postdose biopsies will be collected from patients enrolled to this cohort (unless it is not considered to be safe or otherwise is not feasible) until approximately 5 evaluable paired specimens are collected. Predose biopsies will be collected for all other patients, if feasible. [REDACTED]

*A Simon's two-stage design will test the null hypothesis that the ORR  $\leq 0.10$  versus the alternative that ORR  $\geq 0.25$ . A total of 13 response-evaluable MSS patients will be enrolled in Stage 1. If at least 2 patients respond (PR or better) out of 13 response-evaluable MSS patients, then an additional 21 evaluable MSS patients will be enrolled in Stage 2 (total of 34 response-evaluable MSS patients). If Stages 1 and 2 are completed, a minimum of 6 MSS patients must demonstrate a response (PR or better) to reject the null hypothesis*

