3.2. Control of Type I Error

All statistical analyses are exploratory in nature. Unless otherwise specified, all CIs provided will be at the 95% confidence level.

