5. STATISTICAL METHODOLOGY

5.1. General Methodology

Unless otherwise noted, SAS[®] software (SAS Institute Inc, Cary, NC; v9 or later) will be used for the generation of all tables, graphs, and statistical analyses.

Since this is an open-label clinical trial, descriptive statistics will be employed to analyze the data. Descriptive summaries for continuous variables will include but not be limited to the number of observations, mean, standard deviation, median, minimum, and maximum. Descriptive summaries for categorical variables will include the number and percentage of participants in each category, and time-to-event variables will be summarized by Kaplan-Meier plots, medians, and ranges.

Safety data may be presented by treatment group (INCB001158 monotherapy in Parts 1a and 2, INCB001158 + pembrolizumab in Parts 1b and 3, INCB001158 + pembrolizumab in participants with impaired renal functions in Part 1c) and by INCB001158 dose level.

Efficacy data may be presented by treatment group and dose level in the dose-escalation parts (Parts 1a and 1b) and by treatment group and tumor type for participants in the expansion cohorts (Parts 2 and 3) with data from the renal impairment cohort (Part 1c) included with Part 3.

Data listings will be created to support each table and to present all data collected.

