7.2. Efficacy Hypotheses

Each Simon 2-stage design (Simon 1989) will test the null hypothesis that the true ORR is less than or equal to the clinically insignificant response rate p_0 % against the alternative hypothesis that the true ORR is equal to or greater than the target rate of p_1 %. For each Simon 2-stage design, the value for p_0 is determined by a historical response rate (refer to Protocol Section 15.2).

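### The cohort 3f response test is defined in MSS patients only, but the efficacy-evaluable set named for response analysis in Protocol Section 15 and the SAP carries no MSS restriction

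*SAP*

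**What the plan says.** **The test as the protocol defines it.** In Protocol 5.3, Part 3f, the endpoint is ORR in patients with MSS disease. Stage 1 is 13 response-evaluable MSS patients and continues on 2 or more responders. Stage 2 brings the total to 34 MSS patients, and "a minimum of 6 MSS patients must demonstrate a response (PR or better) to reject the null hypothesis". On the others the section says: "Patients with MSI will also be followed but will not be considered for the primary endpoint for this cohort". It requires microsatellite testing in all 3f patients and expects about 80-90% to be MSS.

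**The set as the analysis sections define it.**
- Protocol 15.3.3: "The Response Evaluable Population includes all patients who received at least 1 dose of study treatment". It adds a baseline scan, plus either a post-baseline scan or a qualifying discontinuation. Microsatellite status is not a condition.
- Protocol 15.1 and 15.4 send the efficacy analysis to the efficacy-evaluable population. The 3f row of Table 15.2-1 gives 10%, 25%, 13 (1) and 34 (5) without saying that these count MSS patients.
- SAP 5.3.4 refers to Protocol 15.3.3 and adds: "The efficacy-evaluable population will be used for the analysis of efficacy data except PFS".
- SAP 7.2 restates the Simon hypotheses. It says that p0 "is determined by a historical response rate (refer to Protocol Section 15.2"), and names no analysis set.
- SAP 7.3.3: "The ORR based on both unconfirmed and confirmed best overall responses will be estimated with 95% CIs".
- SAP 6.1.2 lists MSI status among baseline characteristics that may be summarized. It plays no part in the SAP's response sections.

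**Part 1c.** The Synopsis and Protocol 5.1 count a Part 1c patient towards a Part 3 cohort only if PK/PD criteria are met and the cohort is not already full. SAP 5.1 presents Part 3 efficacy "with data from the renal impairment cohort (Part 1c) included with Part 3" and states no condition.

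**The concern.** The Simon rule and the response rate reported beside it should describe the same patients. For 3f, p0 and both cut-offs refer to MSS disease, which Protocol 5.3 chose because it expects a low response rate to anti-PD-1 therapy alone there. The set that Protocol Section 15 and the SAP assign to response analysis also admits the MSI patients whom Protocol 5.3 excludes.

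An analyst who follows the SAP's numbered references goes to Protocol 15.2 and 15.3.3 and does not meet the MSS rule in either. The resulting 3f ORR would mix two populations and could not be read against p0 = 10% or 6 of 34, which is the protocol's own yardstick for whether the combination is active in this cohort. If MSI patients respond more often than MSS patients, the mixed figure flatters the MSS result.

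**Working it through.** **1. Reproduce the design.** Inputs from Protocol Table 15.2-1, row 3f: n1 = 13, r1 = 1, n = 34, r2 = 5, p0 = 0.10, p1 = 0.25, nominal alpha 0.1 and power 80%.

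P(reject | p) = Σ over x = 2…13 of Bin(x; 13, p) × P(X₂ ≥ 6 − x), with X₂ ~ Bin(21, p).

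- At p = 0.10: 0.0957, with a 0.621 chance of stopping after Stage 1.
- At p = 0.25: 0.811.

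The row reproduces. These operating characteristics belong to 34 MSS patients, because Protocol 5.3 counts only those.

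**2. How many other patients would the stated set contain?** Take the 80-90% MSS share from Protocol 5.3 and treat the remainder as MSI. Reaching 34 MSS patients then needs 34/0.9 = 37.8 to 34/0.8 = 42.5 patients. That is about 4 to 9 patients inside the stated set but outside the protocol's endpoint.

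**3. What happens to the reported ORR?** Let f be the MSI share and q the MSI response rate, with MSS patients at the null rate:

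expected all-comer ORR = 0.10 × (1 − f) + q × f

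The documents give no value for q. It is varied here from 10% to 60% as an assumption.

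| MSI response rate q | f = 0.10 | f = 0.20 |
|---|---|---|
| 10% | 0.09 + 0.01 = 10% | 0.08 + 0.02 = 10% |
| 20% | 0.09 + 0.02 = 11% | 0.08 + 0.04 = 12% |
| 30% | 0.09 + 0.03 = 12% | 0.08 + 0.06 = 14% |
| 60% | 0.09 + 0.06 = 15% | 0.08 + 0.12 = 20% |

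So when MSS disease responds only at the null rate, the tabulated 3f figure is expected to be 0 to 10 points above it. The shift is 1 to 4 points for q of 20-30%.

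**4. Is the restriction restored elsewhere?**
- Protocol 15.1, 15.2, 15.3.3 and 15.4: no.
- SAP 5.1, 5.3.4, 7.2 and 7.3.3: no.
- SAP Appendix A: the Part 3 response tables are labelled with the combined Part 1c and Part 3 efficacy-evaluable population. The labels show no MSS split, but they show no tumor-type split either, although SAP 5.1 says efficacy may be presented by tumor type. Silence in a label is therefore weak evidence about table rows.
- SAP 9.1: no change to protocol-defined analyses is declared, so the Protocol 5.3 rule stands.

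**The case against.** **The protocol governs, and the SAP follows it.** SAP 5.3.4 does what Protocol 15.1, 15.3.3 and 15.4 say. This stands: the omission lies in Protocol Section 15 as much as in the SAP, and both need the correction. It does not remove the conflict with Protocol 5.3.

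**The stakes are limited.** ORR is secondary, SAP 7.1 states that there is no primary efficacy endpoint, and SAP 3.2 says "All statistical analyses are exploratory in nature". Stage decisions are enrolment rules run under Protocol 5.3. Best overall response is listed per participant, so an MSS-only rate could be derived. A shift of 1 to 4 points is also small beside the sampling error: the exact 95% interval for 4 of 38 is 2.9% to 24.8%. All of this lowers the weight of the point. It does not make an all-comer rate comparable with an MSS-only p0.

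**The tables may already be right.** The shells are in a separate document and Appendix A is a guideline. This stands, so what the final tables will show is not known.

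**Two stronger readings that a reader might infer.**
- *The 3f false-positive rate is inflated.* If 6 of 34 were applied to a mixed set with 10-20% MSI patients responding at an assumed 30%, the rejection probability would be 0.178-0.282 instead of 0.096. At an assumed 60% and a 20% share it would be 0.614. No text orders that test: SAP 7.3.3 only estimates ORR with intervals, and the rule in Protocol 5.3 still counts MSS responders.
- *Pooling Part 1c inflates type I error.* If p0 also holds for these patients, counting them within the planned n leaves it unchanged. Inflation needs patients added above n, which the condition that the cohort is not fully enrolled rules out. SAP 5.1 concerns how data may be presented, not who enters a Simon count.

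**Conclusion.** The documents hold two different rules for cohort 3f. Protocol 5.3 tests MSS patients only. Protocol Section 15 and SAP 5.3.4 assign response analysis to a set without that restriction, and SAP 7.2 does not say which set carries the hypotheses. A 3f ORR produced as SAP 5.3.4 is written would not match p0 = 10% or 6 of 34.

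The size rests on the protocol's 80-90% MSS share, on treating the remainder as MSI, and on an assumed MSI response rate. The expected ORR would be 11-12%, 12-14% or 15-20% at MSI rates of 20%, 30% or 60%, against 10% in MSS patients. If MSI patients also respond at 10%, the expected rate does not move, although the denominator is still wrong for the cut-off.

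The conflict itself is clear from the text. Its effect on the final tables is less certain, because the shells were not available. This is worth correcting before the 3f result is reported, but it is not a fault in the sample size.

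The Part 1c matter is minor and one of wording. Table 6.0-1 omits the counting conditions. The Synopsis words the PK/PD condition per patient, while Protocol 5.1 refers back to criteria of which the listed ones concern at least half of the patients. The per-patient reading is the natural one.

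**What to change.** - In SAP 5.3.4 and 7.2, state that the 3f Simon result and the 3f ORR are reported in response-evaluable MSS patients, with MSI gastric/GEJ patients shown separately. Add the same words to Protocol 15.3.3 and to the 3f row of Table 15.2-1.
- If an all-comer 3f ORR is wanted as well, label it supportive. If it is meant to replace the MSS result, record that in SAP 9.1 as a change.
- Minor: say in SAP 5.1 or 7.2 that the pooled Part 1c and Part 3 ORR is supportive, and that only Part 1c patients who qualify under the protocol's existing conditions enter a Simon count, within the planned n. Reconcile the Synopsis, Protocol 5.1 and Table 6.0-1 on those conditions.

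This does not settle whether the confirmed or the unconfirmed response rate carries the Simon result. SAP 7.3.3 reports both, so the same sentence in 7.2 could name one.

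Cost: wording in two documents, one subset flag and one table. Microsatellite status is already tested in every 3f patient, so no extra patients, visits or samples are needed.
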